The incidence of psychological comorbidities in paediatric and young adults with inflammatory bowel disease, and the impacts of mental health conditions on quality of life, disease severity and resource utilisation: a population-based cohort study in the UK

Protocol

NCT number: NCT05206734

Study ID: P043

Document Date: 24th January, 2022

Project highlights

- This study will provide the first UK-based population level analysis of the risk of psychological comorbidities in children, adolescents, and young adults with IBD. The data resulting from this project will provide a measure of the magnitude of any associations. These insights will be valuable for clinicians managing people IBD in this age range; allowing early interventions to be targeted to those most at risk, and potentially reducing the likelihood of more serious future mental health problems.
- The dataset available for use in this project is one of the highest quality primary care data sources available world-wide. It provides the complete coded primary care record with robust data on comorbidities and treatments. In the paediatric population complete records since birth are available for the majority of people.

- Our in-house matching algorithm ensures a higher quality of case-control matching than is available using any other existing statistical software or tools. This is vital to produce reliable data and satisfy external peer review. Matching within a population-based sample has additional advantages over the use of secondary care cohorts, US claim-based datasets, or disease registry datasets. These advantages include minimisation of bias in the control group and the opportunity to select a comparator group affected by another chronic condition.

Background

Inflammatory bowel disease (IBD) comprises 3 main subtypes; ulcerative colitis (UC), Crohn's disease (CD) and IBD unclassified (IBDU). IBD develops at any age; with around 10% diagnosed in childhood.(1) Whilst UC is the most common subtype of IBD in adults, CD is more common in the paediatric IBD (PIBD) population. International trends have confirmed a global rise in the incidence of PIBD; in particular, a steep rise in the incidence of CD.(2) In Scotland, data shows a dramatic increase in PIBD, especially in incidence of CD which has risen 500% over just 40 years.(3)

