Furthering our understanding of the psychosocial sequelae of IBD in children and young adults is particularly important in light of evidence suggesting that symptoms of anxiety and depression may decrease adherence to treatment, thus impacting on longer term disease outcomes,(6) and has been emphasized in a recent call to action issued within gastroenterology to improve understanding and early identification of comorbidities associated with IBD.(10)

To the best of our knowledge, there have not been any large population-based studies assessing the association between psychosocial comorbidities in IBD in

children and young adults and disease related outcomes. The aim of this study is therefore to fill this data gap, and to examine the following objectives.

Such new insights will be valuable for clinicians in optimising patient care for IBD patients; allowing early interventions to be targeted to those most at risk, and potentially preventing the development of more serious mental health problems such as depression; linked to difficulties with medication adherence, and anxiety; which may exacerbate future disease activity.(7, 10)

Ultimately, we anticipate that these data will be useful in understanding the potential cycle and interrelationship between IBD and mental health in children and young adults.

Objectives: Stream 1 – Incidence of mental health conditions

Primary Objectives

- Compare the risk and cumulative incidence of mental health conditions in children and young adults with IBD compared to matched population controls in the primary care setting, stratified by IBD type

Secondary Objectives

- Determine severity of mental health conditions in those with and without IBD (e.g. evidence of self-harm, suicide attempt, behavioural disorders)

Objectives: Stream 2 – Impacts of mental health conditions

Primary Objective:

- Determine the association of mental health conditions in children and young adults with IBD on quality-of-life indicators

Secondary Objectives:

- Compare IBD severity/disease markers in children and young adults with IBD with and without mental health illness

- Compare healthcare resource utilisation in children and young adults with IBD with and without mental health illness

Methods

The study protocol was specified a priori and registered with ClinicalTrials.gov (Study identifier: NCT05206734).

Data source

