The Optimum Patient Care Research Database (OPCRD). This database incorporates pseudonymised primary care records from 700 GP practices distributed across England, Wales, Scotland and Northern Ireland. The current OPCRD cohort size is over 5 million actively registered people, and historic records available for 10.1 million people. The cohort dataset can be enhanced through direct-to-patient and direct-to-care provider questionnaires at additional cost if required.

Study design

The proposed study will use the retrospectively collected data of all eligible patients within the database at the date of data extraction. Within this primary care cohort, all patients with IBD comprising of the three main subtypes; ulcerative colitis (UC), Crohn's disease (CD) and IBD unclassified (IBDU), excluding microscopic colitis, radiation induced enterocolitis and drug-induced enterocolitis, will be identified using diagnostic codes and prescription records. A diagnostic algorithm will be developed to facilitate robust case identification of IBD and IBD subtypes, as well as mental health outcomes.

Statistical methods

We will use standard descriptive statistics (mean, standard deviations, etc) to describe the characteristics of the study cohort.

Recorded sociodemographic characteristics and clinical features

Sociodemographic data will comprise by age group, age at diagnosis, gender, ethnicity, and socioeconomic status. Ethnicity will be categorised as follows to be consistent with the UK official census categories: White, Asian, Black African/Caribbean, Mixed, and Other. The index of multiple deprivation (IMD) will be used as a measure of socioeconomic status. This is derived from patient postcode at the point of data extraction.

Stream 1: Study Cohort

Stream 1: Definition of people with new onset IBD

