The eligible PIBD cases will comprise all incident cases of PIBD over the last decade, we will not follow patients up beyond 01/01/2020 due to changes in patient health behaviour and primary care interactions due to COVID-19. We will extract sociodemographic details for all these cases and matched controls (described below). Sociodemographic data will comprise by age group, gender, ethnicity, and socioeconomic status. Ethnicity will be categorised as follows to be consistent with the UK official census categories: White, Asian, Black African/Caribbean, Mixed, and Other. The index of multiple deprivation (IMD) will be used as a measure of socioeconomic status. This is derived from patient postcode at the point of data extraction.

Stream 1: Definition of matched controls without IBD

We will match each incident case of PIBD with controls (children without IBD) using propensity score matching (matching on the sociodemographic variables list above and matching within primary care practice if numbers allow). People with a known diagnosis of irritable bowel syndrome (IBS) will be excluded from the potential pool of controls. We will compare the incidence of new onset mental health conditions in PIBD and controls using a similar approach to that used by Butwick et al. (2019) in their paper exploring psychiatric disorders in a

PIBD cohort in Sweden.(9) The mental health conditions to be examined are listed in table 1 although there is scope to add to or modify these in discussion with the study authors. For a composite 'any psychological condition' outcome (see Table 1), risk will be stratified by age of PIBD onset and sex.

We will then go beyond the analysis of the Swedish study to estimate the cumulative risk of the 'any psychological condition' composite outcome in PIBD patients compared with controls. This will provide a unique, robust, estimate of the overall mental health burden (prevalence) in PIBD.

Condition	Description
Primary outcomes	
Any psychological condition	A composite of all the chronic psychiatric conditions listed below* (depression, anxiety, eating disorders, body image disorder, attention-deficit disorder, behavioural disorders, adjustment disorder, acute stress disorder, and post-traumatic stress disorder)
Depression	Major recurrent depression or treated depressive episode
Anxiety	Non-phobia related anxiety episodes or disorder
Secondary outcomes	
Self-harm	Any coded episode of deliberate self-harm of any type

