Cox proportional hazards models will be used to compare disease incidence in PIBD cases and controls and also when comparing the associations of baseline features and outcomes within the PIBD cohort. The study start date will be the date of diagnosis of PIBD or, for controls, the date of diagnosis of their matched counterpart. The end of follow-up will be the first of; the point of data extraction (**exact date TBC**), the patient's 25th birthday, date of loss to follow-up (either GP practice deregistration or death). All individuals contributing at least six months of follow-up time in the analysis will be included. Those with existing evidence of the mental health condition prior to baseline will be excluded for analysis of that particular outcome where it would not reoccur, for example if individual has already received a diagnosis of recurrent depressive disorder they would not receive this diagnosis again, although conditions at baseline that can reoccur, such as suicide attempt, would not be excluded. Models will be adjusted for age, gender, socioeconomic status, ethnicity, and other childhood conditions (asthma, atopic dermatitis, allergic rhinitis, thyroid disease, epilepsy, diabetes, cancer, juvenile idiopathic arthritis (JIA) including systemic JIA, systemic lupus erythematosus (lupus), ankylosing spondylitis (AS) and psoriatic arthritis). Statistical significance for analyses will be reported using P values and 95% confidence intervals as appropriate.

Cumulative risk (i.e. prevalence) of the 'any psychological condition' composite outcome will be evaluated up to age 25. Cumulative incidence will be calculated by using methods to estimate risk similar to those recently published when assessing lifetime risk of other chronic conditions in the Lancet.(11, 12) Key outputs will be cumulative risk plots, presenting the cumulative incidence of the outcome by age for PIBD patients compared to controls. At a particular age, the cumulative incidence estimate can be interpreted as the lifetime incidence of the outcome up until the year of age in question. Childhood cumulative risk will be defined as the cumulative incidence at age 18.

Stream 1: Sensitivity analysis

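### The IBS exclusion applies to controls only, carries no date and is never tested, so the Stream 1 comparator is an IBS-free subset of the population named in the objective

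*Combined protocol and SAP*

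**What the plan says.** The primary objective (Objectives: Stream 1) is to compare young people with IBD with the general practice population: "compared to matched population controls in the primary care setting, stratified by IBD type". Project highlights presents matching inside a population sample as a strength: "These advantages include minimisation of bias in the control group".

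Stream 1: Definition of matched controls without IBD then narrows the pool: "People with a known diagnosis of irritable bowel syndrome (IBS) will be excluded from the potential pool of controls". It gives no reason and no date.

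For cases, Stream 1: Definition of people with new onset IBD says "The eligible PIBD cases will comprise all incident cases of PIBD over the last decade". The exclusions attached to IBD identification under Study design concern other forms of colitis: "excluding microscopic colitis, radiation induced enterocolitis and drug-induced enterocolitis, will be identified using diagnostic codes and prescription records". A case with an IBS code therefore stays in.

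Stream 1: Incidence of mental health conditions fixes the index date, "The study start date will be the date of diagnosis of PIBD or, for controls, the date of diagnosis of their matched counterpart", and the covariates, "Models will be adjusted for age, gender, socioeconomic status, ethnicity, and other childhood conditions (asthma, atopic dermatitis, allergic rhinitis". The rest of that list does not include IBS. Stream 1: Sensitivity analysis has one entry, a repeat restricted to controls who consulted in the year before index.

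**The concern.** The same feature, a recorded IBS diagnosis, removes a person from one arm of the comparison and is ignored in the other. If that feature goes with more recorded anxiety, depression or other outcomes, the control rate is lowered and the case rate is not. The hazard ratio then moves upwards, in the direction the study expects to find.

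The missing date adds a second problem. Study design says "The proposed study will use the retrospectively collected data of all eligible patients within the database at the date of data extraction", so whoever builds the pool can see IBS codes entered after a control's index date. Removing a control because of such a code would select on information from follow-up, and follow-up can run to the 25th birthday.

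Every Stream 1 comparison of cases with controls draws on this pool: the three primary outcomes (the composite, depression and anxiety), the secondary outcomes and the cumulative-risk curves to age 25. A reader of the results could not tell how much of a modest hazard ratio came from the exclusion.

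**Working it through.** The documents give no IBS prevalence, no rate of mental illness in people with IBS and no expected event count, so there is no stated figure to reproduce. The check has three steps.

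**1. Is the rule one-sided, undated and untested?**

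| Item | Controls | Cases |
|---|---|---|
| IBS exclusion | Yes | None stated |
| Date attached to the IBS rule | None | Not applicable |
| IBS in the Cox adjustment set | No | No |
| Sensitivity analysis on IBS | None | None |

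Elsewhere the plan does date its rules. Existing mental illness is assessed before baseline, and the consultation restriction covers the year before index. The IBS rule is the one without an anchor.

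**2. Size when IBS controls are removed.** Let h be the rate of new-onset mental illness in people without IBS, p the IBS share of potential controls and r the relative rate in people with IBS.

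- Rate in population controls: h(1 − p) + h·r·p = h[1 + p(r − 1)].
- Rate in IBS-free controls: h.
- The case rate is the same under either choice, so the hazard ratio is multiplied by about 1 + p(r − 1).

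Both p and r are assumptions:

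| p | r = 1 | r = 1.5 | r = 2 | r = 3 |
|---|---|---|---|---|
| 2% | 1.00 | 1.01 | 1.02 | 1.04 |
| 5% | 1.00 | 1.025 | 1.05 | 1.10 |
| 8% | 1.00 | 1.04 | 1.08 | 1.16 |

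**3. What the date changes.** Split the IBS share into p0 (recorded by index) and p1 (recorded later), with the same r for both.

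- Excluding IBS at any time: factor 1 + (p0 + p1)(r − 1).
- Excluding only IBS recorded by index: factor [1 + (p0 + p1)(r − 1)] / [1 + (p1/(1 − p0))(r − 1)].

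For p0 = p1 = 5% and r = 2, the first is 1 + 0.10 × 1 = 1.10 and the second is 1.10 / (1 + 0.0526) = 1.045. A simulation at a true hazard ratio of 1, with 5 years of follow-up and a baseline hazard of 0.02 per year (both assumed), gives nearly the same values:

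| p0 | p1 | r | By index only | At any time |
|---|---|---|---|---|
| 1% | 2% | 1.5 | 1.005 | 1.015 |
| 2% | 3% | 2 | 1.018 | 1.048 |
| 5% | 5% | 2 | 1.042 | 1.095 |
| 5% | 5% | 3 | 1.081 | 1.185 |

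Dating the rule removes more than half of the inflation in each scenario, but not all of it. The remainder comes from excluding IBS in controls alone, and only an analysis that keeps those controls shows its size.

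**The case against.** The strongest reply is that a known diagnosis, in a sentence about a pool of potential controls, most naturally means known when the pool is formed, and each control's start date is the matched case's diagnosis date. A reader might infer that the plan selects controls on their future records. The documents do not support that: retrospective extraction makes it possible, but nothing says it is intended. What stands is that the text allows both readings, and two analysts could build different pools.

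Second, the size rests wholly on assumed inputs. The value 1.16 is the extreme corner of the range, and at a low IBS share the effect is 1% or less. This is correct, and the exclusion would not by itself explain a large hazard ratio.

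Third, a reader might infer that every primary hazard ratio is pushed upwards. That needs r above 1 for each outcome separately, including a composite that contains attention-deficit, behavioural and eating disorders. For outcomes that would not recur, people with prior evidence are removed, so the relevant r is for new onset and may differ from any general excess in people with IBS. The documents do not supply it.

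Fourth, with p between 2% and 8%, 92% to 98% of potential controls remain, and keeping undiagnosed IBD out of the controls would be a fair aim, although the plan does not state it. That supports a dated exclusion. It does not support leaving its effect unexamined.

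**Conclusion.** The point holds as a cheap improvement. On the text, the exclusion is confined to controls, undated, unadjusted and untested, and the comparator differs from the one named in the primary objective. Upward bias is conditional on IBS being associated with more new-onset recorded mental illness, which the documents do not state. Under that assumption the hazard ratio is inflated by about 1.05 at p = 5% and r = 2, and by 1.01 to 1.16 over p = 2–8% and r = 1.5–3. It is larger if later IBS codes also count. This is a possible modest bias of unknown size, not a demonstrated one. Neither deliberate selection on future records nor inflation of all primary outcomes can be concluded from the documents.

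**What to change.** 1. In Stream 1: Definition of matched controls without IBD, limit the exclusion to IBS recorded on or before the index date, so that no control is removed on later information.
2. In Stream 1: Sensitivity analysis, prespecify a repeat of the primary Cox models and the cumulative-risk curves with IBS controls retained. This carries most of the weight, because dating the rule does not make it symmetrical between cases and controls.
3. Report the number of controls removed for IBS, and describe the main comparator as *controls without prior IBS* wherever results are given.

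The cost is one phrase and one extra run on data already held. The downside is that the analysis retaining IBS controls may include a few people with undiagnosed IBD, which should be said when it is reported.

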Suicide attempt	Any episode of suicide attempt and suicide related codes, including deliberate medication overdose
Other chronic psychiatric conditions	Eating disorders, body image disorder, attention-deficit disorder (ADHD), behavioural disorders, adjustment disorder, acute stress disorder, schizophrenia, bipolar disorder and post-traumatic stress disorder (PTSD)
Others	Problems with sleep

*this excludes conditions which are potentially single events i.e. self-harm or suicide attempt. (See Appendix 1 – Table s3 for Read Codes and SNOMED Codes

for mental health conditions, Table s4 for mental health condition algorithms and Table s5 for WHO ICD-10 mental health conditions).

Stream 1: Incidence of mental health conditions

The study will report the incidence of each mental health condition overall in the PIBD cases and controls, and adjusted hazard ratios to test the association between PIBD and risk of the same mental health conditions. Within the PIBD cohort we will examine the relationship between PIBD age of onset, sex, ethnicity, and social deprivation and the 'any psychological condition' composite outcome.

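### The six-month follow-up rule makes inclusion depend on survival and registration after the index date, so early deaths (including suicides) and events in early leavers drop out of both streams

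*Combined protocol and SAP*

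**What the plan says.** **Stream 1** (section on incidence of mental health conditions). Time zero is defined thus: "The study start date will be the date of diagnosis of PIBD or, for controls, the date of diagnosis of their matched counterpart". Follow-up ends at the first of the data extraction date, "the patient's 25th birthday, date of loss to follow-up (either GP practice deregistration or death". The next sentence is the rule: "All individuals contributing at least six months of follow-up time in the analysis will be included". It is worded as inclusion; exclusion of everyone with less is implied. The model is named in the same paragraph: "Cox proportional hazards models will be used to compare disease incidence in PIBD cases and controls".

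**Stream 2** (statistical methods). The same sentence appears. The index date is 01/01/2015, and follow-up ends at the first of 01/01/2020, the 25th birthday, deregistration or death. The models are Poisson, negative binomial or zero-inflated Poisson, with log person-years as an offset.

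**Outcomes.** Table 1 defines the Stream 1 secondary outcome of suicide attempt as "Any episode of suicide attempt and suicide related codes, including deliberate medication overdose". In Stream 2, parasuicide is one of the affective symptoms among the quality-of-life indicators, which are that stream's primary objective. Its code list (Appendix 3, sTable 3.1) contains codes for completed suicide, by named method and not otherwise specified.

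The clock is not restarted at six months in either stream. The one planned sensitivity analysis, in Stream 1, concerns controls who do not attend their practice.

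**The concern.** Whether a person belongs to the cohort should be known at time zero. Here it depends on what happens in the next six months: the person must stay alive and registered. Anyone who does not is removed together with any event already recorded.

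This conflicts with the plan's own outcomes. Completed suicide is coded as an event in Stream 2, and death ends follow-up, so a suicide in months 0-6 can never be counted. In Stream 1 the months just after a new IBD diagnosis are of direct interest for new-onset mental illness, and severity, including self-harm and suicide attempt, is a stated secondary objective. At stake are the suicide and self-harm results and, if the rule were applied more widely than its context suggests, the incidence figures as well.

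**Working it through.** The plan gives no sample size, event rate or event count, so there is no planned figure to reproduce. The rule is first set against the follow-up definition and then sized under stated assumptions.

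**Step 1: who fails the rule.**
- Death in months 0-6: follow-up ends, so the person is always excluded.
- Deregistration in months 0-6: excluded, with any earlier event.
- 25th birthday or administrative end within six months of index: excluded, but this is known at the index date and is not selection on the future.
- Non-fatal event in months 0-6 in someone who stays registered for six months: the outcome event is not in the end-of-follow-up list, so the person and the event are kept.

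Call this natural reading A. Reading B takes follow-up time in the analysis to mean Cox time, which stops at the event. Everyone with a first event before six months would then be dropped.

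**Step 2: size under reading A.** Assumptions: index dates uniform over 10 years, deregistration at 8% a year in both groups and unrelated to outcome.
- Share of people with less than six months of registered time: 1 - exp(-0.08 x 0.5) x (1 - 0.5/10) = 1 - 0.961 x 0.95 = 0.087.
- They contribute about 0.25 years each within months 0-6, against 0.5 for the rest. Their share of that person-time is 0.087 x 0.25 / (0.087 x 0.25 + 0.913 x 0.5) = 0.046.
- With a constant hazard, months 0-6 hold about 13% of events in this setting, so the loss is about 0.046 x 0.13 = 0.6%.

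**Step 3: simulated Cox fits.** Same assumptions, 4 controls per case, 60,000 cases. Percentages are events lost.

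| Control rate per 1000 person-years | HR months 0-6 / later | HR, no rule | HR, A | HR, B |
|---|---|---|---|---|
| 20 | 1.5 / 1.5 | 1.50 | 1.49 (0.6%) | 1.51 (13.0%) |
| 20 | 3 / 1.5 | 1.65 | 1.64 (0.8%) | 1.45 (16.3%) |
| 20 | 5 / 1.5 | 1.96 | 1.94 (1.0%) | 1.51 (19.3%) |
| 20 | 3 / 1.0 | 1.29 | 1.28 (0.8%) | 1.02 (17.1%) |
| 40 | 1.5 / 1.5 | 1.52 | 1.52 (0.5%) | 1.53 (13.6%) |
| 40 | 3 / 1.5 | 1.71 | 1.70 (0.8%) | 1.50 (17.2%) |
| 40 | 5 / 1.5 | 1.98 | 1.96 (0.9%) | 1.50 (20.6%) |
| 40 | 3 / 1.0 | 1.28 | 1.27 (0.8%) | 1.00 (17.8%) |

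Under A, 0.5-1% of events are lost and the HR moves by at most 0.02. Under B with a constant HR of 1.5 (first row) the HR holds, but rates fall from 30.1 to 26.4 (cases) and from 20.1 to 17.6 (controls) per 1000 person-years.

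**Step 4: fatal outcome.** Assumed control rate 0.5 per 1000 person-years, HR 3 in months 0-6 and 1.5 later. Both readings remove every death in months 0-6, which is 15.8% of fatal events, and the HR falls from 1.73 to 1.49.

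**Step 5: share of first events in months 0-6, the loss under B.** With constant hazard h and T years of follow-up, the share is (1 - exp(-0.5h)) / (1 - exp(-hT)).
- h = 0.02, T = 5: 0.00995 / 0.0952 = 0.105.
- h = 0.06, T = 3: 0.0296 / 0.1647 = 0.179.

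The other two corners (h = 0.02, T = 3; h = 0.06, T = 5) give 0.171 and 0.114.

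**The case against.** The strongest reply is that the rule does little to the main results, and on the natural reading this is right. The Stream 1 primary outcomes are the composite, depression and anxiety. The composite leaves out self-harm and suicide attempt, and the losses are of the order in Step 2. Early suicide deaths may be very few; excluding all of them is a statement about the rule, not about a known count. In Stream 1 the use of completed-suicide codes is itself inferred from the wording of Table 1, because those codes are printed in the quality-of-life list (sTable 3.1) and not in the mental health list (sTable 2.1). Stream 2 is a prevalent cohort, so the argument about the months after a new diagnosis does not apply there.

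A reader might go further and infer that the rule deletes every early event, because a person in a Cox model stops contributing time at the event. The documents do not support this as the literal meaning. The sentence just before the rule lists what ends follow-up, and the outcome is not in the list. Stream 2 uses the identical sentence with count models that include repeated events, where the Cox argument does not arise. The words can bear that meaning in Stream 1, and the plan does not rule it out, but it is the less natural reading.

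A reader might also infer that the rule breaks matched sets. The plan states a covariate-adjusted Cox model and no stratification by set, so harm by that route is not shown.

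What stands is the selection on survival and registration after index, the certain loss of deaths in months 0-6 and of events in early leavers, and the absence of any sensitivity analysis of the rule.

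**Conclusion.** The point holds, with modest weight. In both streams inclusion is conditional on post-index survival and registration. The certain harm falls on the suicide and self-harm outcomes: a secondary outcome in Stream 1, and part of the primary quality-of-life objective in Stream 2. On the natural reading the Stream 1 primary outcomes are barely affected (0.5-1% of non-fatal events, HR change 0.02 or less). That result assumes the rates in Step 3 and deregistration that is alike in cases and controls and unrelated to outcome. If people leave a practice because of early mental illness, the loss could be larger.

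The large shifts in the last column of the table should not be read as the expected effect. They need reading B and, for the HR, an assumed early excess that fades; no document gives such hazards. They show why the meaning of follow-up time should be fixed in writing: under B, incidence and cumulative risk would be understated even if the HR were constant.

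**What to change.** Delete the six-month post-index requirement in both streams. Include every eligible person from the index date and let each contribute time until the event or actual exit, however short. Censoring in the Cox model and the person-years offset in Stream 2 already deal with short follow-up. If a minimum registration period is wanted for data quality, require it before the index date, for cases and controls alike.

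If the rule is kept at all, use it only as a sensitivity analysis, and state that the outcome event does not end follow-up for this purpose. Also settle the Stream 1 administrative end, because it decides who can reach six months: the cohort definition says "we will not follow patients up beyond 01/01/2020", while the follow-up paragraph uses an extraction date still to be confirmed.

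The cost is one sentence per stream and a small number of added people with very short follow-up.
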